8.2.2. Overdose

Overdose, as defined for this protocol, refers to lenalidomide dosing. On a per dose basis, an overdose is defined as the following amount over the protocol-specified dose of lenalidomide assigned to a given subject, regardless of any associated AEs or sequelae.

- >10% over the protocol-specified dose.

On a schedule or frequency basis, an overdose is defined as anything more frequent than the protocol-required schedule or frequency.

Complete data about drug administration, including any overdose, regardless of whether the overdose was accidental or intentional, should be reported in the CRF. See Section 11 for the reporting of AEs associated with overdose.

8.3. Method of Treatment Assignment

All subjects will be enrolled into the study using an IWRS. The Investigator or designated site staff will be assigned password protected, coded identification numbers that give them authorization to log into the IWRS. At screening, the Investigator or designated staff will log into the IWRS and provide the requested identifying information for the subject. The IWRS will then confirm the assignment of a 2-part unique subject number. The first part is the center number and the second part is one of a series of numbers allocated to subjects at that center. Once assigned to a subject, the subject number will not be reused. If the subject is not enrolled into the study the IWRS must be notified.

Prior to enrolling a subject, written ICF/IAF must be obtained, all screening evaluations must be completed, and eligibility criteria must be verified by the Sponsor. Once these actions have been completed, the Investigator or designated staff will log into the IWRS and confirm that the subject fulfills all the inclusion and exclusion criteria. The IWRS will assign an enrollment number to the subject which will be used to identify the subject in the study.

8.4. Packaging and Labeling

The label(s) for IP will include Sponsor name, address and telephone number, the protocol number, IP name, dosage form and strength (where applicable), amount of IP per container, lot number, expiry date (where applicable), medication identification/kit number, dosing instructions, storage conditions, and required caution statements and/or regulatory statements as applicable. Additional information may be included on the label as applicable per local regulations.

8.5. Investigational Product Accountability and Disposal

Accountability for lenalidomide administered during the course of the study is the responsibility of the Investigator (or designee).

Investigational clinical supplies must be received by a designated person at the study site and kept in a temperature-controlled location. Lenalidomide should be stored according to the storage conditions described on the packaging label and in a locked, safe area to prevent unauthorized access.

The Investigator (or designee) is responsible for taking an inventory of each shipment of lenalidomide received, and comparing it with the accompanying lenalidomide accountability form. The Investigator (or designee) will verify the accuracy of the information on the form, sign and date it, retain a copy in the study file, and return a copy to Celgene.

The investigational site must maintain accurate records demonstrating dates and amounts of lenalidomide received, to whom it was administered (subject-by-subject accounting), and accounts of any lenalidomide accidentally or deliberately destroyed or returned. Accurate recording of all lenalidomide administration will be made in the appropriate section of the subject's CRF and source documents.

Unless otherwise notified, all lenalidomide both used and unused must be saved for IP accountability. After IP accountability has been completed by the monitor, Celgene (or designee) will review with the Investigator and relevant site personnel the process for lenalidomide return, disposal, and/or destruction including responsibilities for the site versus Celgene (or designee).

8.6. Investigational Product Compliance

All IP used by subjects will be documented by study site personnel and accurate recording of all lenalidomide used will be made in the appropriate section of the subject's CRF and source documents.

9. CONCOMITANT MEDICATIONS AND PROCEDURES

9.1. Permitted Concomitant Medications and Procedures

All supportive care is permitted, including but not limited to:

- Platelet transfusions
- Intravenous immunoglobulin
- RBC transfusions
- G-CSF per American Society of Clinical Oncology (ASCO) guidelines
- Leukapheresis
- Exchange transfusions
- Hemodialysis
- Hydration
- Allopurinol
- Sodium bicarbonate (NaHCO₃)
- Dexamethasone ophthalmic solution or isotears
- Pyridoxine
- Antiemetics
- Chlorhexidine solution
- Pain medications
- Antibiotics
- Anti-herpetics
- Anti-fungals
- Hydroxyurea is permitted prior to start of lenalidomide (Cycle 1 Day 1) and through Day 14 of Cycle 1 if needed to control leukocytosis. Administration will be at the discretion of the investigator.

9.2. Prohibited Concomitant Medications and Procedures

- Other chemotherapy or IP than what is specified in the protocol
- Live vaccines
- Biological therapies
- Other investigational agents

10. STATISTICAL CONSIDERATIONS

10.1. Overview

All statistical analyses will be descriptive. There will be no formal statistical comparisons due to the study being single-armed and due to a low sample size.

Secondary endpoints can only be analyzed and reported based on subjects who have had at least 6 months from study enrollment. The final analysis will be conducted once the last remaining subject in the Follow-up Phase has completed up to 5 years from the last subject's first dose.

10.2. Study Population Definitions

Response Rate population

The response rate (RR) population shall consist of all subjects classified as evaluable for the primary endpoint, ie, all subjects fulfilling the eligibility criteria, having received at least one dose of the lenalidomide and having at least one disease assessment post enrollment or having treatment failure before an assessment can be conducted. The RR population shall be applied to the analysis of the primary endpoint.

Intention to treat population

The intention to treat (ITT) population shall consist of all enrolled subjects regardless of whether they received lenalidomide. The ITT population shall be applied to all treatment activity-based primary and secondary endpoints.

Safety population

The safety population consists of all subjects receiving at least one dose of lenalidomide and shall be applied to all safety based endpoints.

Pharmacokinetic population

The PK population consists of all subjects receiving at least one dose of lenalidomide and having at least one measurable lenalidomide concentration.

10.3. Sample Size and Power Considerations

Under Simon's Optimal two stage design with a 5% significance level and 80% power, assuming a lower boundary of interest in the response rate of 10% and an upper boundary of interest in the response rate of 25%, a total of 43 evaluable subjects are required for the evaluation of the primary endpoint; 18 in Stage 1 and an additional 25 in Stage 2.

If less than 3 of 18 evaluable subjects in Stage 1 achieve a morphologic response (either CR or CRi) within a maximum of 4 cycles then the study will terminate, otherwise the study shall continue as planned and enrollment of an additional 25 subjects shall continue into Stage 2.

If, at the final analysis, less than 8 of 43 evaluable subjects in both Stage 1 and 2 achieve a response (either CR or CRi) within a maximum of 4 cycles then it will be concluded that lenalidomide, at the dose level tested, does not have sufficient activity in pediatric AML (second

or greater relapse or refractory). However, should at least 8 of the 43 evaluable subjects achieve a response (either CR or CRi) then it will be concluded that lenalidomide, at the dose level tested, demonstrates activity in pediatric subjects with AML (second or greater relapse or refractory) to allow further investigation. Up to 4 additional subjects may be included to account for subjects found to be unevaluable for the primary endpoint (eg, incorrect diagnoses, not having a disease assessment post screening, or who discontinued prior to receiving lenalidomide therapy). The first 43 subjects enrolled and evaluable for the primary endpoint analysis will be used to assess the primary endpoint.

10.4. Background and Demographic Characteristics

Subjects' age, height, weight, and baseline characteristics will be summarized using descriptive statistics, while gender, race and other categorical variables will be provided using frequency tabulations. Medical history data will be summarized using frequency tabulations by system organ class and preferred term.

10.5. Subject Disposition

Subject disposition (analysis population allocation, entered, discontinued, along with primary reason for discontinuation) will be summarized using frequency and percent for both Treatment and Follow-up Phases. A summary of subjects enrolled by site will be provided. Protocol deviations will be summarized using frequency tabulations.

10.6. Efficacy Analysis

10.6.1. Primary endpoint

Morphologic complete response rate (CR or CRi) rate within 4 investigational product cycles

The primary endpoint is the morphological complete response rate within a maximum of 4 cycles of treatment. Morphological complete response is defined as CR or CRi. These response criteria will be assessed according to the revised AML IWG Criteria (Cheson, 2003).

The morphological complete response rate is defined as the total number of subjects with morphological complete response observed within the first 4 cycles of study therapy (regardless of whether the CR/CRi is observed at the end of Cycle 1, 2, 3 or 4) over the total number of subjects evaluable for this endpoint (maximum likelihood estimator). The CR/CRi does not need to be present at the end of Cycle 4 if observed before this time for the subject to be considered as having achieved a complete response with regards to the primary endpoint. The corresponding Clopper Pearson 95% confidence interval will be calculated for the response rate. The primary analysis of this endpoint will be based upon the ITT population and the Response Rate population. Decision making with regard to continuation to Stage 2 and at the end of Stage 2 will be based on responses within the Response Rate population.

10.6.2. Secondary endpoints

Overall Response Rate

Overall response rate defined as the proportion of subjects with CR, CRi or PR among all subjects evaluable for ORR assessment. The ORR rate at the end of Cycles 1, 2, 3, 4, 8 and 12 will be categorized, and the rate will be calculated by dividing the number of subjects completing each given cycle of interest. The corresponding Clopper Pearson 95% confidence interval will be calculated for the response rate at the end of each pre-specified cycle.

Disease Assessment Outcome

Disease assessment outcome at the end of Cycles 1, 2, 3, 4, 8 and 12 of lenalidomide administered shall be categorized according to the Cheson criteria (Cheson, 2003). The response rate for each of the best response criteria will be calculated as the total number of subjects in a given category at each time point over the number of subjects completing each corresponding cycle. The corresponding Clopper Pearson 95% confidence interval will be calculated per response category at the end of each pre-specified cycle.

Durable Response Rate

Durable response rate is defined as the proportion of subjects achieving a bone marrow confirmed CR/CRi lasting at least 3 months or until transplantation if earlier among all subjects evaluable for the durable response rate assessment. The corresponding Clopper Pearson 95% confidence interval will be calculated for the durable response rate.

Duration of Response

Duration of response is defined as the time from date of the first observed response (CR, CRi or PR) until morphologic relapse, molecular/cytogenetic relapse, or death only for subjects achieving a response. Subjects alive and leukemia-free at the time of the statistical analysis will be censored at the time of their last disease assessment. The median DoR time along with the corresponding 95% confidence interval based on Greenwood's standard error will be calculated using Kaplan-Meier methods. The proportion of subjects remaining without a DoR event at 6, 12 and 24 months will also be presented. Should the number of subjects considered for inclusion in DoR analysis fall below a third of the total sample size, the DoR shall be analyzed descriptively due to the low number of subjects available for analysis. Duration of response shall be analyzed both allowing for censoring of subjects at time of HSCT and without censoring of subjects at the time of HSCT.

Transplantation Rate

The proportion of subjects undergoing a transplant of any kind during the conduct of this study will be calculated over the total number of subjects enrolled into this study. The corresponding Clopper Pearson 95% confidence interval for the proportion of transplantations shall be calculated. Proportions shall also be calculated based on whether the transplantation is first, second, or subsequent transplants.

Subject/blast Characteristics Correlating With Response

Laboratory results obtained at diagnosis and relapse (peripheral WBC and blast count, bone marrow blast percentage, cytogenetics, molecular alterations, etc.) will be evaluated in association with response parameters by means of Pearson's rank correlation.

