Appendix D: Modified International Working Group AML Response Criteria

Hematologic Response According to IWG Criteria for AML	
Category	Definition
Morphologic Complete Remission (CR)	
The following conditions should be met:
 
 • Absolute neutrophil count (ANC) \geq 1000/μL and platelets \geq100,000/μL without transfusions and/or exogenous growth factor support (ie, no transfusion or exogenous growth factor within 7 days of assessment). • Bone marrow with < 5% blasts and evidence of trilineage hematopoiesis. • No evidence of extramedullary disease.
Morphologic Complete Remission With Incomplete Blood Count Recovery (CRi)	
 • ANC < 1000/μL. • Platelets < 100,000/μL or > 100,000/μL without platelet recovery (requiring transfusion within 7 days of assessment). • Bone marrow with < 5% blasts and evidence of trilineage hematopoiesis. • No evidence of extramedullary disease.
Partial Remission (PR)^a	
 • ANC \geq 1000/μL and platelets \geq 100,000/μL without transfusions and/or exogenous growth factor support (ie, no transfusion or exogenous growth factor within 7 days of assessment). • Bone marrow with 5% to 25% blasts and at least a 50% decrease in bone marrow blast percent from baseline. • No evidence of extramedullary disease.

Hematologic Response According to IWG Criteria for AML	
Category	Definition
Treatment Failure	
Resistant Disease: Patient survives ≥ 7 days post-therapy and failed to achieve CR, CRi, or PR with persistent AML in blood or bone marrow.
 
Aplasia: Patient survives ≥ 7 days post-therapy; death while cytopenic, with aplastic bone marrow.
 
Indeterminate cause:
 
 • Patients who die < 7 days post-therapy. • Patients who die > 7 days post-therapy with no peripheral blood blasts, but no bone marrow examination. • Patients who do not complete the first course of therapy. 
Morphologic relapse after CR or CRi:
 
 • the reappearance of $> 5\%$ blasts in the peripheral blood, or • a single finding of $> 15\%$ blasts in the bone marrow. 
All of the above occurrences should be attributed to relapse following CR or CRi and not attributable to another cause (eg, bone marrow regeneration after consolidation therapy).
 
Molecular or cytogenetic relapse: Reappearance of molecular or cytogenetic abnormality.

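### Duration of response includes PR responders, but for a subject whose best response is PR, losing that response is not an event and no censoring rule covers it

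*Protocol*

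**What the plan says.** DoR is a secondary endpoint in Protocol 3.2. Section 10.6.2 starts the clock at the first CR, CRi or PR and runs it "until morphologic relapse, molecular/cytogenetic relapse, or death only for subjects achieving a response". Its only general censoring rule is: "Subjects alive and leukemia-free at the time of the statistical analysis will be censored at the time of their last disease assessment". The analysis is to be done with and without censoring at HSCT. Kaplan-Meier median and 6-, 12- and 24-month proportions are planned, but DoR is only described if responders number less than a third of the sample.

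Appendix D supplies the terms:

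- Morphologic relapse is headed "Morphologic relapse after CR or CRi", and the entry adds: "All of the above occurrences should be attributed to relapse following CR or CRi".
- The other relapse entry reads: "Molecular or cytogenetic relapse: Reappearance of molecular or cytogenetic abnormality". It does not name CR or CRi.
- PR requires: "Bone marrow with 5% to 25% blasts and at least a 50% decrease in bone marrow blast percent from baseline".
- Resistant disease, under treatment failure, applies to a patient who "failed to achieve CR, CRi, or PR with persistent AML in blood or bone marrow".

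The SAP has no DoR analysis. DoR is absent from its objectives (3.2), endpoints (4.2.2) and efficacy sections (10.2.1 to 10.2.6), and Section 16 does not list it among the changes or dropped analyses.

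**The concern.** The population and the event list do not match. PR responders enter the analysis, but the disease events are written for subjects who reached CR or CRi, or whose marker cleared. When blasts rise again after a PR, the response has ended clinically but not in the DoR calculation. The subject cannot be censored under the stated rule either, because a marrow with 5% to 25% blasts is not leukemia-free, still less one that has worsened.

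The programmer must therefore improvise, and both obvious choices lengthen DoR. Follow-up to death counts time after failure as response, including time on later therapy, since Protocol 6.23 continues follow-up regardless of new anticancer treatment. Censoring at the last assessment treats a known loss of response as an unknown one.

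**Working it through.** **1. The plan's own figure.** The documents give no DoR median, event count or precision to reproduce. The only design calculation is the Simon design in Protocol 10.3. The probability of declaring activity is Σ over x = 3 to 18 of P(Bin(18, p) = x) · P(Bin(25, p) ≥ 8 − x). This gives 0.0480 at p = 0.10 and 0.8003 at p = 0.25, matching the stated 5% and 80%. DoR does not enter it.

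**2. Possible courses set against the rules of 10.6.2 and Appendix D.**

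| Course | DoR event | Censoring rule |
|---|---|---|
| CR/CRi, then morphologic relapse | Yes | Not needed |
| PR, later CR/CRi, then morphologic relapse | Yes | Not needed |
| Best response PR, marker clears and returns | Yes, at the marker's return | Not needed |
| Best response PR, lost without marker relapse, dies | Only at death | Not needed |
| Best response PR, lost without marker relapse, alive | None | None |
| Best response PR, still in PR at analysis | None, correctly | None, since not leukemia-free |

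Rows four to six are the gap; rows four and five lengthen DoR.

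**3. Is loss of PR already defined elsewhere?** Protocol 6.20.4 re-assesses PR subjects at suspected treatment failure, and SAP 10.2.2 equates anything less than PR with treatment failure. But treatment failure as such is not a DoR event. Its resistant-disease entry requires never having reached PR, and its relapse entry follows CR/CRi. No entry describes a lost PR.

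**4. One hypothetical subject.** PR at month 1, lost at month 3, death at month 9. Counting the loss: 3 − 1 = 2 months, event. Following to death: 9 − 1 = 8 months, event. Censoring at the assessment that showed the loss: 2 months, but no event.

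**5. Size under assumed inputs.** The documents give none of these, so all are assumptions: exponential times, median 3 months to loss of response for every responder, median m = 3 or 6 months from loss to death, and a PR-only share s. Write x = 2^(−t/3).

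- Loss counted as an event: S(t) = x.
- Followed to death, m = 3: S(t) = (1 − s)x + s·x(1 + t·ln 2/3).
- Followed to death, m = 6: S(t) = (1 − s)x + s(2√x − x).
- Censored at loss: S(t) = x^(1 − s), so the median is 3/(1 − s).

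At 6 months x = 0.25. For s = 0.5 and m = 3: 0.5 × 0.25 + 0.5 × 0.25 × (1 + 1.386) = 0.423. Solving S(t) = 0.5 gives the medians.

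| s | Loss counted | To death, m = 3 | To death, m = 6 | Censored |
|---|---|---|---|---|
| 0 | 3.0 mo; 25% | 3.0; 25% | 3.0; 25% | 3.0; 25% |
| 0.25 | 3.0; 25% | 3.9; 34% | 4.2; 37.5% | 4.0; 35% |
| 0.50 | 3.0; 25% | 5.0; 42% | 6.0; 50% | 6.0; 50% |
| 0.75 | 3.0; 25% | 6.1; 51% | 8.3; 62.5% | 12.0; 71% |

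Entries are median months and percent event-free at 6 months. A simulation of 200,000 subjects per scenario agrees to about 0.03 months.

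**6. When Kaplan-Meier applies.** 43/3 = 14.3, so at least 15 responders are needed (16 if the total is taken as 47, since 47/3 = 15.7). P(Bin(43, ORR) ≥ 15) is 0.096 at an ORR of 25%, 0.292 at 30% and 0.564 at 35%. The ORR values are assumptions; the protocol states 10% and 25% only for CR/CRi.

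**The case against.** The strongest reply is that the affected group may be small or empty and the output mostly descriptive. Much of that stands. PR here requires neutrophil and platelet recovery without support. A subject who passes through PR to CR/CRi has a valid relapse event, and with no PR-only responders there is no bias. At the ORR rates tried up to 30%, fewer than 15 of 43 subjects would more likely than not respond, so Kaplan-Meier figures would not be produced. The reply does not remove the point: a descriptive listing or summary still uses each subject's duration, derived under the same event rule.

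A reader might infer several stronger things that the documents do not support:

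- That relapse of every kind presupposes CR/CRi, so loss of PR can never coincide with an event. This is literal only for morphologic relapse; a PR subject whose marker cleared and returned has an event. That event is the marker's return, however, not the loss of PR.
- That every PR responder who progresses gets a wrong duration. Rows two and three of the table in the working show otherwise.
- That the text makes the duration run to death. For a living subject who has lost PR the text is silent; running to death is one reading, censoring at the last assessment another.
- That a lost PR is already an Appendix D treatment failure, so naming that category would suffice. Sections 6.20.4 and SAP 10.2.2 use the term that way, but no Appendix D entry defines it for a lost PR.

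**Conclusion.** The gap is real and should be closed. For subjects whose best response is PR, loss of that response is neither an event nor covered by censoring, and both ways of filling the silence overstate DoR whenever such a loss precedes death. The direction follows from the definitions. The size cannot be derived from the documents: it grows with the PR-only share and is zero without such subjects. The medians in the working (3.9 to 12.0 months against a true 3.0, for PR-only shares of 25% to 75%) are illustrations resting on the assumed exponential times.

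Individual durations are affected in any case. The Kaplan-Meier median and the 6-, 12- and 24-month proportions are affected only with at least 15 responders of 43. It would be wrong to infer any effect on the trial's decision: the primary endpoint uses CR/CRi only, and the stage 1 and final rules do not use DoR. Nor does the SAP's silence show that DoR was deliberately abandoned, since Section 16 lists dropped analyses and DoR is not among them.

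**What to change.** Choose one of two definitions in Protocol 10.6.2:

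1. Restrict DoR to subjects who reach CR or CRi, starting at the first CR/CRi.
2. Keep PR responders and add an explicitly defined loss of PR as an event alongside relapse and death: a response assessment worse than PR after PR, recorded as treatment failure. Because Protocol 6.22 lets the marrow be omitted at discontinuation when peripheral blasts are collected, state how loss of PR is determined in that case.

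Under either option, censor every responder without an event at the last disease assessment, leukemia-free or not, and keep the planned analyses with and without censoring at HSCT.

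Then add DoR with this definition to SAP 3.2, 4.2.2 and 10.2, or record in SAP Section 16 that DoR is dropped and why.

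The cost is a few sentences. No new visits are needed, because Protocol 6.20.4 already calls for an IWG response at every marrow assessment and at suspected treatment failure after PR. The downside is that the reported DoR may be shorter, and option 1 gives no duration for PR-only responders.
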